Appendix G: Adverse Events of Special Interest

Notes:

[1]: The preferred terms listed in the table is based on the MedDRA version applicable at the time of finalization of the SAP. If the MedDRA version is upgraded at the time of the analysis, the corresponding preferred terms based on the upgraded version will be used in the analysis of adverse events of special interest.

Table 12-7 MedDRA Preferred Terms for Event of Special Interest	
Adverse event of special interest	MedDRA preferred terms [1]
Elevated transaminase	Alanine aminotransferase abnormal, Alanine aminotransferase increased, Aspartate aminotransferase abnormal, Aspartate aminotransferase increased, Transaminases abnormal, Transaminases increased, Liver function test abnormal, Liver function test increased, Hypertransaminasaemia, Hepatic enzyme abnormal, Hepatic enzyme increased
Rash	Rash, Rash erythematous, Rash macular, Rash maculo-papular, Rash maculovesicular, Rash vesicular, Rash pruritic, Rash follicular, Rash pustular, Nodular rash, Drug eruption, Fixed eruption, Urticaria, Urticaria papular, Urticaria vesiculosa, Urticarial dermatitis, Rash morbilliform, Rash papular, Rash papulosquamous, Rash rubelliform, Rash scarlatiniform , Drug hypersensitivity, Type IV hypersensitivity reaction, Dermatitis, Dermatitis atopic, Epidermolysis, Skin toxicity, Dermatitis allergic, Dermatitis exfoliative, Dermatitis exfoliative generalised, Erythema multiforme, Exfoliative rash, Mucocutaneous rash, Acute generalised exanthematous pustulosis, Cutaneous vasculitis, Urticarial vasculitis, Dermatitis bullous, Drug reaction with eosinophilia and systemic symptoms, Epidermal necrosis, Oculomucocutaneous syndrome, Skin exfoliation, Skin necrosis, Stevens-Johnson syndrome, Toxic epidermal necrolysis, Toxic skin eruption, Perioral dermatitis, Vasculitic rash, Immune-mediated dermatitis, Penile rash, SJS-TEN overlap, Erythrodermic atopic dermatitis, Scrotal rash

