13.1.1.2 Clinically Significant Assessments

Study assessments including laboratory tests, ECGs, physical examinations, and vital signs will be assessed and those deemed to have clinically significant worsening from baseline will be documented as an AE. When possible, a clinical diagnosis for the study assessment will be

provided, rather than the abnormal test result alone (e.g., urinary tract infection, anemia). In the absence of a diagnosis, the abnormal study assessment itself will be listed as the AE (e.g., bacteria in urine or decreased hemoglobin).

An abnormal study assessment is considered clinically significant if the subject has 1 or more of the following:

- Concomitant signs or symptoms related to the abnormal study assessment
- Further diagnostic testing or medical/surgical intervention
- A change in the dose of study drug or discontinuation from the study

Repeat testing to determine whether the result is abnormal, in the absence of any of the above criteria, does not necessarily meet clinically significant criteria. The determination of whether the study assessment results are clinically significant will be made by the investigator.

A laboratory value that is Grade 4 will not automatically be an SAE. A Grade 4 laboratory value will be an SAE if the subject's clinical status indicates a life-threatening AE.

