13.1.1.3 Documentation of Adverse Events

All AEs will be collected from the time the ICF is signed until the subject completes study participation, as defined in Section 9.1.7.

All subjects will be queried, using nonleading questions, about the occurrence of AEs at each study visit. When possible, a constellation of signs and/or symptoms will be identified as 1 overall event or diagnosis. All AEs for enrolled subjects will be recorded in the CRF and source document. AEs for subjects who are screened but not subsequently enrolled will be recorded only in the subject's source documents. The following data will be documented for each AE:

- Description of the event
- Classification of "serious" or "nonserious"
- Date of first occurrence and date of resolution (if applicable)
- Severity
- Causal relationship to study drug(s)
- Action taken
- Outcome
- Concomitant medication or other treatment given

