9.4.9 Supportive Safety Analysis

9.4.9.1 Adverse Events of Special Interest

For this study, elevated transaminase events and rash events, as determined by MedDRA preferred terms in [Appendix G](#), are considered as adverse events of special interest.

For treatment-emergent elevated transaminase events and rash events, the following categories will be summarized by treatment group:

- Subjects with events
- Subjects with events by maximum severity
- Subjects with events leading to treatment discontinuation
- Subjects with events leading to treatment interruption
- Subjects with serious events
- Subjects with related serious events
- Subjects with events leading to death
- Duration of events
- Time-to-onset of first event

In addition, for treatment-emergent rash events, these categories will be summarized for the following subgroups:

- Sex (male, female)
- Female subjects with concomitant hormonal therapy (Yes, No)

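### The elevated-transaminase event of special interest is selected by laboratory-finding terms only, so a liver event that a site records only as a diagnosis is not counted in it

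*SAP*

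**What the plan says.** SAP section 9.4.9.1 names two adverse events of special interest: "elevated transaminase events and rash events, as determined by MedDRA preferred terms" given in Appendix G. No other route into either group is described.

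Table 12-7 lists 11 terms for the group labelled Elevated transaminase. The first six are "Alanine aminotransferase abnormal, Alanine aminotransferase increased, Aspartate aminotransferase abnormal, Aspartate aminotransferase increased, Transaminases abnormal, Transaminases increased". From the sixth term to the end the list reads "Transaminases increased, Liver function test abnormal, Liver function test increased, Hypertransaminasaemia, Hepatic enzyme abnormal, Hepatic enzyme increased", which adds the other five.

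For each group, section 9.4.9.1 plans nine summaries by treatment group: any event, maximum severity, discontinuation, interruption, serious, related serious, fatal, duration, and time to first onset.

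Protocol section 13.1.1.2 says how an abnormal assessment becomes an adverse event. When possible, the site gives a clinical diagnosis in place of the bare test result. The fallback is: "In the absence of a diagnosis, the abnormal study assessment itself will be listed as the AE". Section 13.1.1.3 adds a related instruction: "When possible, a constellation of signs and/or symptoms will be identified as 1 overall event or diagnosis".

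**The concern.** The two documents pull in different directions. The protocol's recording rule moves an event away from the laboratory term once a diagnosis is available. The SAP's term list recognises only the laboratory term. A site that follows section 13.1.1.2 and records a transaminase rise solely as hepatitis or drug-induced liver injury produces an event that Table 12-7 does not pick up, while an unexplained rise of any size is picked up.

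The rash group in the same table is built differently. It starts with simple rash terms and continues to named diagnoses such as Stevens-Johnson syndrome and toxic epidermal necrolysis. For skin, the list runs from sign to diagnosis; for liver, it stops at the sign, and no other group covers diagnosed liver injury.

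At stake is how the group's own table reads. A zero in its serious or fatal row could mean that there was no such event, or that the event was recorded under a term not on the list. The table alone cannot tell the reader which.

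**Working it through.** The plan states no figure on this point, so there is none to reproduce. The check is a comparison of texts, followed by a simple statement of scale.

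**1. The term list (SAP Appendix G, Table 12-7).** There are 6 + 5 = 11 terms. Ten end in *abnormal* or *increased*; the eleventh is Hypertransaminasaemia. Screening for words that mark a diagnosis (injury, hepatitis, jaundice, failure, cholestasis, cirrhosis, necrosis, toxicity) gives 0 of 11. The table's footnote carries the terms over to a newer MedDRA version but does not widen their scope.

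**2. The recording rule (Protocol 13.1.1.2) against the list.**

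| How the site records the event | Matches Table 12-7? |
|---|---|
| No diagnosis; enzyme rise recorded as the event | Yes |
| Diagnosis recorded, and a separate enzyme event also recorded | Yes, through the enzyme event |
| Diagnosis recorded alone | No |

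Only the third line is affected. The protocol permits it and, when a diagnosis is possible, prefers it.

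**3. What is lost and what remains.** An event in the third line is absent from all nine summaries in SAP 9.4.9.1. Elsewhere the SAP still provides:
- graded bands for ALT, AST, alkaline phosphatase and bilirubin, and the combined criterion of ALT or AST >3×ULN with total bilirubin >2×ULN (Table 12-3);
- ALT or AST >3×, >5× and >8×ULN (Table 12-6);
- scatter plots of maximum ALT and AST against maximum total bilirubin (section 9.4.2);
- tables by System Organ Class and Preferred Term for all, Grade 3/4, related, serious, related serious, discontinuation, interruption and fatal events, plus listings (section 9.4.1).

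So seven of the nine summaries (any, severity, discontinuation, interruption, serious, related serious, fatal) have a counterpart in the general tables, but term by term and not as one pooled hepatic count. The remaining 9 − 7 = 2, duration and time to onset, are planned only in 9.4.9.1.

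**4. Scale.** The planned ELX/TEZ/IVA arm is 125 subjects (SAP 7.2). Each subject missed lowers that arm's incidence for the group by 1/125 = 0.8 percentage points; two subjects lower it by 2/125 = 1.6 points.

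The documents give no rate of liver events recorded only as a diagnosis. As an assumption, let that rate be p per subject. The chance of at least one among 125 is 1 − (1 − p)^125:

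| Assumed p | Chance of at least one |
|---|---|
| 0.2% | 22% |
| 0.5% | 47% |
| 1% | 72% |
| 2% | 92% |

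These figures show only how the answer moves with p; none of the four rates comes from the documents.

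**The case against.** The strongest reply is that the group does what its name says. It is labelled Elevated transaminase, not liver injury, and enzyme terms fit that label. The interruption rule in Protocol 9.8.1 is also driven mainly by ALT and AST multiples. This stands: the list is not wrong for its label. The gap is that no group of special interest covers diagnosed liver injury, while the rash group does extend to severe skin diagnoses.

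Second, a reader might infer that diagnosed liver injury disappears from the liver safety results. It does not. The outputs in step 3 show it, and the laboratory ones do not depend on how the event was coded. A subject with a measured ALT >8×ULN appears in the threshold tables whatever term the site chose. The only table that the SAP marks as intended for labeling is one of those laboratory tables. One reservation remains: local laboratory results are allowed in some circumstances (Protocol 11.6.2 and the COVID-19 addendum), and the SAP does not say whether they enter the threshold tables.

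Third, a reader might infer that the serious and fatal rows must come out empty, because "A laboratory value that is Grade 4 will not automatically be an SAE". The next sentence of the protocol makes such a value serious if the subject's clinical status indicates a life-threatening event, and section 13.1.2.1 adds hospitalization and other criteria. An event under an enzyme term can therefore fill the serious rows. That the summary is biased toward looking mild is possible but not shown.

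Fourth, the recording rule is qualified by *when possible*. The grouping instruction in 13.1.1.3 speaks of signs and symptoms, not laboratory values, and neither section says that an enzyme event already recorded must be withdrawn once a diagnosis is made. So only some events are exposed.

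Finally, safety is analysed descriptively, with no testing (SAP 9.4). No endpoint or hypothesis test depends on this table.

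**Conclusion.** The point holds in a limited form. A liver event recorded only as a diagnosis, as Protocol 13.1.1.2 prefers when possible, is not counted in the elevated-transaminase summary of SAP 9.4.9.1. For such an event, duration and time to onset are summarised nowhere else, and there is no pooled hepatic count. Its occurrence, severity and seriousness remain visible term by term in the general tables, and any recorded laboratory excursion remains visible in the threshold outputs, subject to the reservation about local results.

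The size is 0.8 percentage points of a 125-subject arm for each subject missed. The number missed cannot be estimated from the documents and may be zero. The conclusion rests on one assumption: that some sites record a diagnosis with no separate enzyme event. It does not support a claim that liver risk is hidden. This is a mismatch between a recording rule and a term list, and it is cheap to close.

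**What to change.** Amend SAP Appendix G before database lock and unblinding; SAP section 4 already provides for amendments approved before lock.

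- Add to Table 12-7 a hepatic-diagnosis group: drug-induced liver injury, liver injury, hepatocellular injury, hepatotoxicity, hepatitis, jaundice, hepatic failure, and the equivalents in the MedDRA version used.
- Summarise it with the same rows as in 9.4.9.1, once alone and once combined with the present 11 terms.
- Keep the 11-term Elevated transaminase set as a labelled subset, so that it stays comparable with other studies.

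Choosing the terms while still blinded avoids any suggestion that they were picked after results by arm were seen.

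The cost is a longer term list and extra row blocks in the output. No new data are needed. The small downside is that a hepatitis unrelated to drug may be counted, in either arm; reporting the diagnosis group separately from the 11 terms keeps that visible.
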